Intervention Checklist: See attached—Inpatient Firearms Study—MD Checklist for Intervention Review.

Outcomes:

The primary outcome is the change in parent/legal guardian's behavior over the past 30 days with respect to how often they asked whether or not there are guns in the home when their child/children goes to play in another's person's home, as indicated by a Likert scale assignment of an ordinal value (1-5, 1= never, 2=rarely, 3=sometimes, 4=most of the time, 5=always).

Secondary outcomes will include:

- Change in the primary outcome (intention to ask noted above) between the intervention groups (Be SMARTalone vs. Be SMART + MD)
- Demographic factors associated with primary outcome
- Description of general knowledge on firearm safety of parents/legal guardians of patients in our community
- Description of attitudes about firearm safety of parents/legal guardians of patients in our community
- Description of general practices regarding firearm safety of parents/legal guardians of patients in our community
- Description of parents attitudes regarding physicians discussing firearm safety with them

Data Analysis:

The main objective of the data analysis is to assess within each intervention group whether the general parental practice of asking about firearms in the homes of others when their children go to play is increased after the intervention. A secondary objective is to perform a head-to-head comparison of the magnitude of the intervention effects between the groups. Our pilot data revealed the proportion of the population who either "always" or "most of the time" ask about firearms in the homes of others when their children went to play was 50%. With a sample size of 60 subjects in the Be SMART alone group, the study will have 80% power using the McNemar's test with a two-sided alpha=0.05 level to detect an absolute increase of 20% between the pre-intervention and post-intervention responses (i.e. raising the proportion of those who either "most of the time" or "always" ask about firearms in the homes of others when their children went to play from 50% to 70%). For the

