Be SMART + MD group, we expect the pre- post intervention effect to be larger, i.e., increase from 50% before the intervention to 80% after the intervention in the proportion of the population who either “most of the time” or “always” asked about firearms. With a sample size of 60 subjects in the Be SMART + MD group , the study will have greater than 95% power to detect this difference using the McNemar’s test with a two-sided alpha=0.05 level. We expect minimal change in the pre- and post-survey responses in the control group. For the comparisons between treatment arms, we will focus on the subset of parents who initially responded that they were not likely to ask about firearms before the intervention (expected to be ~ 50% of parents) and assess whether the proportion who changed their response to “most of the time” or “always” after the intervention is greater in those who were in either of the Be SMART groups compared to the control group. With 60 subjects in each of the 3 study groups, the study will have 80% power to detect an increase in this proportion from 10% in the control group (which is a conservative assumption) to 40% in either the Be SMART alone or Be SMART + MD group using a two-sample test of proportions and a two-sided alpha=0.05 level.

We anticipate the majority of the subjects enrolled will complete the inpatient portion of the study, however, we estimate up to 20% will not be able to be reached by phone for the 30 day follow up call. Therefore given that our primary outcome is based on behavior assessed at the 30 day follow up phone call, we will add to each study group 15 patients to give each study group at total of 75 patients, and the overall study population will be 225 patients.

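### Is the stated 80% McNemar power for a rise from 50% to 70% with 60 parents overstated?

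*Combined protocol and SAP*

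**What the plan says.** In the Data Analysis section, the first paragraph sizes the within-group comparison: "With a sample size of 60 subjects in the Be SMART alone group, the study will have 80% power using" "McNemar's test with a two-sided alpha=0.05 level to detect an absolute increase of 20% between the pre-intervention and post-intervention responses". The effect is a move from 50% to 70% in the share of parents in the top two frequency categories. For the Be SMART + MD group the expected move is 50% to 80%, again with 60 parents, and the plan says "the study will have greater than 95% power to detect this difference".

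The same paragraph then powers a separate comparison between arms. It is restricted to parents who do not usually ask at baseline ("expected to be ~ 50% of parents"), and the target is an "increase in this proportion from 10% in the control group (which is a conservative assumption) to 40% in either the Be SMART alone" or the Be SMART + MD group. For the control arm the plan says: "We expect minimal change in the pre- and post-survey responses in the control group".

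The next paragraph allows for up to 20% loss by the 30-day call and raises each group from 60 to 75. The plan gives no discordant proportion, pre-post correlation or reversal rate (baseline askers who later do not ask). It does not say which version of McNemar's test will be used.

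**The concern.** McNemar's test uses only the parents who change category. The before and after percentages fix the difference between the two kinds of change but not their total, and the total drives the variance. A power figure quoted from 50% and 70% alone therefore cannot be checked, and this figure supports the 60 evaluable and 75 enrolled parents per group.

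The between-arm paragraph seems to make matters worse. The stated 80% corresponds to about 52% of non-askers converting and 12% of askers reverting, whereas the between-arm calculation uses 40% conversion. If minimal change in the control group means that its 10% conversion is cancelled by 10% reversal, and that reversal rate is carried into the Be SMART alone group, within-arm power comes out near 65%. On that reading the within-group comparison, which the plan calls its main objective, would be underpowered.

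**Working it through.** **Inputs.** From Data Analysis: n = 60, two-sided alpha 0.05, 50% to 70% (d = 0.20), about 50% non-askers at baseline, and conversion of 10% (control) and 40% (either Be SMART group). Let p01 be the share of all parents who start asking and p10 the share who stop, with discordance psi = p01 + p10 and d = p01 − p10.

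**Formula.** Power = Φ[(d√n − 1.96√psi) / √(psi − d²)].

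**1. Reproducing the 80%.** The stated inputs leave psi open, so solve for it. At psi = 0.318: d√n = 0.20 × 7.746 = 1.549; 1.96 × √0.318 = 1.105; √(0.318 − 0.04) = 0.527. Then (1.549 − 1.105)/0.527 = 0.84, and Φ(0.84) = 0.80. The cells are p01 = (0.318 + 0.20)/2 = 0.259 and p10 = (0.318 − 0.20)/2 = 0.059. As shares of each baseline half, these are 52% conversion and 12% reversal. Across versions of the test and formula, the value giving 80% runs from 0.29 to 0.35.

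**2. Power over the range of psi (50% to 70%, n = 60).** The minimum is 0.20, because p10 cannot be negative.

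| psi | Normal formula | Exact test |
|---|---|---|
| 0.20 (no reversals) | 95% | 99% |
| 0.25 | 89% | 89% |
| 0.30 | 82% | 80% |
| 0.32 | 80% | 76% |
| 0.40 | 70% | 64% |
| 0.50 (independence) | 60% | 53% |

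Under independence p01 = 0.50 × 0.70 = 0.35 and p10 = 0.50 × 0.30 = 0.15, and 80% power would need 96 parents.

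**3. The plan's conversion figure.** 40% of the 50% non-askers is p01 = 0.40 × 0.50 = 0.20. With a net gain of 0.20, p10 = 0, so psi = 0.20 and power is 95%. The two paragraphs are compatible at this point, and the result is above the stated 80%.

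**4. Where 65% comes from.** Add 10% reversal among the 50% askers: p10 = 0.10 × 0.50 = 0.05. Then psi = 0.25 but d = 0.15, so the effect is 50% to 65%. Power = Φ[(0.15 × 7.746 − 1.96 × 0.50)/√(0.25 − 0.0225)] = Φ(0.182/0.477) = Φ(0.38) = 65% (exact test 58%). The discordance here, 0.25, is below the 0.318 limit. Power falls because the effect is smaller, not because more parents change. At the stated 50% to 70%, 65% power would require psi of about 0.44.

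**5. Be SMART + MD group (50% to 80%, d = 0.30).** Power exceeds 95% for psi from 0.30 (the minimum) to about 0.457. Independence (psi 0.50) gives 93%.

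**6. Follow-up.** 60/0.80 = 75, so 60 is the number analysed at the largest anticipated loss. If all 75 were reached, power at psi 0.40 would be 79% rather than 70%.

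**The case for a change.** The best case for acting is that the margin is thin and the comparison is the main objective. The 80% tolerates reversal by about 12% of baseline askers. With 15% reversal (psi = 0.20 + 2 × 0.075 = 0.35) power is 76%, and with 20% (psi = 0.40) it is 70%. The outcome is a self-reported five-point frequency cut between its third and fourth levels, with follow-up by telephone, so some crossing in both directions is plausible. The same 60 parents are also justified by different conversion scenarios. The + MD group cannot reach 80% with 40% conversion, since 0.50 + 0.20 = 0.70; it needs at least 0.30/0.50 = 60%. A reader of a null result would want to know whether power was nearer 95% or 60%.

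Much of this stands as description. The discordance is unstated, the McNemar version is unstated, and power is sensitive to both.

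The step to an error does not stand. The 10% in the plan is a conversion rate among control non-askers, offered as a conservative value. Minimal change is not zero change: with no reversals the control arm would rise by only 0.10 × 0.50 = 5 points. Carrying an inferred reversal rate into an arm that has just received firearm-safety education adds a further assumption. The 40% is attached to either intervention group even though the + MD group is expected to do better, so it reads as a detectable difference for a separate test, not a forecast for each arm. Two power statements for two tests need not share one joint scenario. Independence is a harsh benchmark: it supposes that a parent's baseline answer says nothing about the answer a month later, and that 30% of askers stop.

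**Conclusion.** The concern does not call for a change. The 80% is incompletely documented rather than miscalculated: by the normal formula it holds for discordance from 0.20 to about 0.32, with the upper limit between 0.29 and 0.35 depending on the version used. The greater-than-95% claim holds up to about 0.457. It is not established that the within-arm power is overstated by about 15 points, or that the two power paragraphs are incompatible. The 65% belongs to a smaller effect (50% to 65%) with a reversal rate the plan does not give, so writing it into the plan would replace an undocumented figure with a less well supported one.

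What remains is a missing planning detail. Supplying it would alter neither the enrolment of 75 per group nor the analysis. McNemar's test works from the discordant pairs actually observed, and its significance level does not depend on the planning value. An analyst can choose the exact or asymptotic form in the ordinary way, and a null result can be read from the observed discordance and an interval for the paired difference. The conclusion assumes the plan's 50% baseline and 20-point effect. The documents give no data on how many parents would revert, so true power for that effect could lie below 80% if discordance exceeded about 0.32, reaching about 60% at independence.

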firearms since this has been proven to be an ineffective strategy.⁸ It also provides counseling for non-firearm-owning families, as it recommends asking about unsecured firearms prior to playdates. Thus, it can serve as a simple, universal counseling tool for parents who are gun-owning and non-gun-owning. It has not been formally evaluated as an educational tool.

Children's hospitals may be a good place to counsel on firearm safety. Large children's hospitals draw patients from surrounding areas that may include rural, suburban, and urban areas. A hospital-based intervention would allow outreach to children of all ages. The "free time" patients spend in the hospital, while either recovering or waiting for procedures or results, may make patients amenable to receiving such counseling. The inpatient setting has been successfully utilized to provide educational interventions to parents of hospitalized children on other topics, best studied in the area of smoking cessation.⁹⁻¹² Walley et al. utilized the "Smoking and Kids Don't Mix" video for parents/caregivers of hospitalized children, demonstrating successful reported behavior changes in parents/caregivers to reduce second- and third-hand smoke.¹² To our knowledge no other study has utilized the inpatient setting to address issues related to firearm safety counseling and education.

The primary aim of the study is to determine whether the Be SMART campaign delivered to parents in a hospital setting leads to an improvement in knowledge, attitudes, and practices about firearm safety. The secondary aim is to determine whether the intervention is more effective when delivered with physician face-to-face counseling in addition to with video and written materials, or with standardized video and written materials alone.

Study Aims:

- 1) To measure whether parents' knowledge, attitudes, and practices change after a brief educational intervention on gun safety
- 2) To measure the knowledge, attitudes, and practices of parents in a tertiary care children's hospital regarding firearm safety practices
- 3) To compare the efficacy of two methods of delivery of counseling: a video alone versus a video plus a physician-delivered intervention
- 4) To measure whether these changes in practices are sustained one month after the intervention

METHODS

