For within-group data analysis, we will use standard descriptive statistics to summarize the data and McNemar’s test or the paired T- test to assess the significance of pre-post intervention differences in binary and continuous outcomes, respectively. In secondary analysis, we will analyze the parents who responded before the intervention: “rarely”, “never”, or “sometimes” to ask about firearms in the homes of others when their children went to play groups and compare across interventions the proportion who changed their response to “most of the time” or “always” after the intervention using the chi-square or Fisher’s exact test. We will also use logistic regression models to analyze factors associated with the likelihood to ask about firearms in the homes of others when children go to play.

Informed Consent:

Parents of hospitalized children will be approached for written informed consent on the inpatient service by trained research personnel. Our form asks for consent to participate in the pre-intervention and post-intervention surveys, and to participate in the educational intervention, including randomization to one of the three study groups (Be SMART alone, Be SMART+ MD discussion, or the control group). Additionally the consent asks for permission to collect phone numbers in order to contact the parent/legal guardian one month later for a follow up survey. If consent is granted, a brief questionnaire will be administered followed by the intervention and very brief follow up survey.

Risks:

We do not anticipate any risks to the participants. Any information obtained that would permit identification of a participant, it will be held strictly confidential, will be used only for the purpose of this study, and will not be disclosed or released to others.

Benefits:

This study will examine knowledge, attitudes, and practices of parents/legal guardians regarding firearm safety and tobacco smoke exposure. While there may be no direct benefits to the participants themselves, through the educational intervention, they may increase their knowledge regarding gun safety and tobacco smoke exposure, particularly related to children, and may decide to change some of their own practices related to either or both firearm safety issues and tobacco smoke exposure and their children.

Privacy:

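### Does the plan leave the comparison of Be SMART alone with Be SMART + MD without a test?

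*Combined protocol and SAP*

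**What the plan says.** All references are to the combined protocol and SAP.

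- **Study Aims**, aim 3: "To compare the efficacy of two methods of delivery of counseling: a video alone versus a video plus a physician-delivered intervention".
- **Outcomes**, first secondary bullet: "Change in the primary outcome (intention to ask noted above) between the intervention groups (Be SMARTalone vs. Be SMART + MD".
- **Data Analysis**, opening: "A secondary objective is to perform a head-to-head comparison of the magnitude of the intervention effects between the groups".
- **Data Analysis**, between-arm power text: among parents not likely to ask at baseline (about half), the question is whether the proportion who convert "is greater in those who were in either of the Be SMART groups compared to the control group". Power is 80% for a rise from 10% in control "to 40% in either the Be SMART alone or Be SMART + MD group", with 60 subjects per group, by a two-sample test of proportions at two-sided 0.05.
- **Data Analysis**, sample-size paragraph: 60 per group is raised to 75 for up to 20% loss, "given that our primary outcome is based on behavior assessed at the 30 day follow up phone call".
- **Data Analysis**, methods paragraph: for parents answering never, rarely or sometimes at baseline, the plan will "compare across interventions the proportion who changed their response to" one of the top two categories, by chi-square or Fisher's exact test.

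**The concern.** The head-to-head question is the reason for having two Be SMART arms, but no sentence ties a specific contrast to it. The power text speaks only of comparisons with control. The methods sentence could mean one three-arm test, a set of pairwise tests, or the two Be SMART arms alone.

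The readings do not answer the same question. A control-only reading gives no result for the first secondary outcome. A three-arm test responds to any Be SMART effect over control, so it can be significant when the physician adds nothing. Only a two-arm test addresses aim 3. If the contrast is open, it could be picked after the data are seen.

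The endpoint also looks unsettled. The Outcomes bullet describes the primary outcome as an intention, whereas the outcome defined just above it is behavior over the past 30 days. Two surveys follow the intervention, one in hospital and one at a month, so a response after the intervention could come from either.

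**Working it through.** **Inputs.** From Data Analysis: 60 evaluable per arm (75 × 0.80 = 60); about 50% non-askers, so 60 × 0.5 = 30 per arm; conversion 10% in control and 40% in either Be SMART arm; two-sided 0.05.

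**The plan's own figure.** For 10% against 40% with n = 30 per arm:

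- Unpooled z: SE = √[(0.10×0.90 + 0.40×0.60)/30] = √0.011 = 0.105; 0.30/0.105 − 1.96 = 0.90; power 81.6%.
- Pooled z: 78.0%. Arcsine: 80.3%.
- Exact enumeration of the uncorrected chi-square: 79.6%.
- Fisher's exact: 70.5%.

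The stated 80% reproduces without continuity correction.

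**Three-arm against two-arm.** All 31 × 31 × 31 outcomes (31 × 31 for two arms) were enumerated at n = 30 per arm. The three-arm statistic is X² = n Σ(p̂ᵢ − p̄)² / [p̄(1 − p̄)] on 2 df; the two-arm statistic is the 1-df version for Be SMART alone against + MD. Entries are the chance of p < 0.05.

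| Control / alone / + MD | Three-arm | Two-arm |
|---|---|---|
| 10 / 40 / 40% | 81.8% | 4.9% |
| 10 / 30 / 30% | 48.0% | 4.9% |
| 20 / 40 / 40% | 39.4% | 4.9% |
| 5 / 40 / 40% | 95.9% | 4.9% |
| 10 / 50 / 50% | 96.8% | 5.2% |
| 40 / 40 / 40% | 5.1% | 4.9% |

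The Fisher versions at 10/40/40 give 80.7% and 2.6%. Letting the subset sizes vary as Binomial(60, 0.5) gives 80.7% for the three-arm chi-square.

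**If the physician does help.** The plan's targets are 50% to 70% (alone) and 50% to 80% (+ MD). Write post = 0.5(1 − r) + 0.5c, where c is conversion among non-askers and r is reversion among askers. The plan does not state r, so two values are shown.

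- r = 0: c = (0.70 − 0.50)/0.5 = 40% and (0.80 − 0.50)/0.5 = 60%. Three-arm 98.5%, two-arm 35.0% (Fisher 25.7%).
- r = 0.10: c = (0.70 − 0.45)/0.5 = 50% and (0.80 − 0.45)/0.5 = 70%. Three-arm 99.9%, two-arm 35.1% (Fisher 25.9%). The 95% CI half-width is 1.96 × √[(0.25 + 0.21)/30] = 0.243.

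**What the text already settles.**

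| Element | Where it is fixed |
|---|---|
| Contrast | Outcomes: "between the intervention groups (Be SMARTalone vs. Be SMART + MD"; also aim 3 and the head-to-head objective |
| Subset | Methods paragraph: baseline never, rarely or sometimes |
| Binary endpoint | Methods paragraph: change to the top two categories |
| Test | Methods paragraph: chi-square or Fisher's exact |
| Form of between-arm test | Power text: two-sample test of proportions |
| Time point | Sample-size paragraph: primary outcome at the 30-day call |

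Only the sentence joining the first row to the others is absent. Outcomes uses the term intervention groups for exactly the two Be SMART arms, so the methods sentence can be read as covering that pair. The power text on comparisons with control justifies the sample size; it does not withdraw an objective stated just before it.

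**The case for a change.** The best case for a change is that the question is central, the wording admits a three-arm test, and the choice matters. In the table rows with a Be SMART effect over control but no physician effect, the three-arm test is significant about 8 to 20 times as often as the two-arm test (39.4/4.9 = 8.0; 95.9/4.9 = 19.6). Even with a real physician effect of the planned size, the two-arm test has only about 35% power, so there would be a temptation to report the test that comes out significant. A few words would remove the choice at no cost in participants or data.

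The arithmetic stands, and so does the observation that the methods sentence does not name its arms. The consequence does not follow. At 10/40/40 the arms truly differ, so a three-arm rejection is correct for the hypothesis it tests. Harm requires an analyst to present that p-value as evidence on the physician, against an outcome that names the two arms. The plan mentions no omnibus test. With the subset, cut-point and test family already written down, the room for later choice is narrow.

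The intention wording is a real slip, but the bullet points back to the outcome defined above it, which is behavior, and the sample-size paragraph places that outcome at the 30-day call.

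**Conclusion.** The concern does not call for a change. The plan names the contrast in one place and the test, subset and cut-point in another; an analyst following both compares Be SMART alone with Be SMART + MD directly at the 30-day call. The missing link is a drafting gap, and the reference to intention is a clerical slip.

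The 81.8% against 4.9% holds for 30 non-askers per arm with 10% control and 40% in both Be SMART arms. Among the no-physician-effect cases with a Be SMART effect over control, the three-arm figure runs from 39.4% to 96.8%. It shows that a three-arm test would be the wrong tool for aim 3, not that the plan chose it. The stated 80% power against control is sound (79.6% by exact chi-square). The direct comparison will be imprecise, at about ±24 points if conversion is 50% and 70%; that reflects the sample size and would not improve with clearer wording.
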